8.4.2. Analysis of secondary endpoints

Student's t-test or Mann-Whitney U-test will be applied to test the comparison between A and S Groups for the time to identify the epidural space, duration of the epidural space localization procedure, the distance from the skin to the epidural space, and the distance from the needle tip to dura.

Number of attempts, number of the occurrence of false positive, and number of change insertion segment will be compared between A and S groups using Fisher's exact test.

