5.2.4. Physical examination

A complete physical examination will be performed at the screening visit, including the examination of general appearance, skin, cardiovascular, pulmonary, abdomen, neurological system and musculoskeletal/joints. Height and weight will be also collected at Visit 1.

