5.2.5. Epidural space localization procedure

Subjects will undergo the surgical procedure using epidural space localization in a medical center with appropriate facilities and by appropriately trained personnel.

Epidural space localization planning will be completed before the epidural space localization. The plan should be recorded, and the records should include surgery name, insertion segment.

During epidural space localization, the subject are in the lateral position. After cleaning and draping the area, a local anesthetic is infiltrated at the insertion site of epidural needle.

Anesthesiologist inserted the epidural needle at least 3cm to pass the subcutaneous tissue. Pull out the stylet and attach the filled EpiFaith syringe. In Group A, the EpiFaith syringe is filled with air; in Group S, the EpiFaith syringe is filled with saline. Then, push the plunger to create a continuous pressure inside the syringe. When the needle arrived the epidural space, due to LOR occurred, the piston of EpiFaith syringe will move forward. The clear visual signal can warn the operator the localization of needle tip. After the detection of LOR, the catheter will be inserted though the needle. When the catheter can protrude from the needle tip at least 3cm, which can be identified by the graduations on its surface, the test dose (2 ml of 2% lidocaine) of anesthetic will be injected. After injection for 15min, the cold sensation test will be performed, by comparing the perception of cold of alcohol sponges between the blocked dermatomes and face. The tests will be bilaterally, and repeated 3 times in 3 difference dermatomes on each side.

If the visual signal occurs but the catheter cannot be inserted to protrude the needle tip at least 3 cm, which means the false positive occurs.

If the catheter is inserted successfully and the test dose of anesthetic is injected, but the result of cold sensation test shows the perception of cold exists in the blocked dermatomes by cold sensation test and exclude the reason is due to dose and drug failure, which also means the false positive occurs.

If the inadvertent dural puncture occurs, the success of epidural localization will be recorded failed. There is no necessary to record all secondary outcome. The physician can use the traditional LOR syringe or other method to compete the procedure.

The process of epidural space localization will be simultaneously recorded by video.

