8. STATISTICAL METHODS

8.1. Planned Sample Size

Considering the recommendation given by Lancaster, Dodd &Williamson. A total of 60 subjects (30 subjects per group) will be required in this study to obtain parameters such as ratio, mean and standard deviation which will be used in a sample size calculation for the full-scale trial, and to estimate the rate of participants who drop out of the trial.

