8.4. Efficacy Assessment

Statistical analyses will be reported using summary tables, graphs, and data listings. Analysis are performed with SPSS, Version 20.0 (IBM Corporation, Armonk, NY, USA). The analysis population will be summarized by A and S groups. For categorical variables, frequencies and percentages will be summarized; continuous data will be shown as descriptive statistics. The variables within a normal distribution will be compared using Student's t-tests, and those without a normal distribution will be compared using the Mann-Whitney U test. The number of patients will be compared between the groups using the Fisher's exact test. All information will be summarized and presented in statistical analysis tables. As for data of efficacy and safety variables, no imputation method is applied.

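### Times and distance are compared by valid but unadjusted tests although height and weight are recorded before randomization, so precision may be lost on these secondary endpoints

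*Combined protocol and SAP*

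**What the plan says.** Section 8.4.2 (Analysis of secondary endpoints) names Student's t-test or the Mann-Whitney test, which "will be applied to test the comparison between A and S Groups for the time to identify the epidural space", for procedure duration and for the distance from skin to epidural space. Section 8.4 gives the rule for choosing between them: normally distributed variables get the t-test, and "those without a normal distribution will be compared using the Mann-Whitney U test". Sections 8.3 to 8.5 contain no adjusted model. Section 3.4 describes blocked 1:1 randomization and states no stratification by body size or spinal level.

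Two kinds of covariate data are collected. Section 5.2.4 states: "Height and weight will be also collected at Visit 1". The schedule of assessments places randomization at Visit 2, so body size is a true baseline measure. Section 5.2.5 asks for a localization plan before the procedure: "The plan should be recorded, and the records should include surgery name, insertion segment".

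Section 8.1 sets the size: "A total of 60 subjects (30 subjects per group) will be required in this study". Its purpose is "to obtain parameters such as ratio, mean and standard deviation which will be used in a sample size calculation for the full-scale trial".

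**The concern.** Skin-to-epidural distance is an anatomical depth that includes subcutaneous tissue, so it plausibly varies with body size. The two times may do so as well. An unadjusted comparison leaves that variation in the error term. With 30 per arm and no stratification, a chance difference in BMI between the arms also adds noise to the estimated air-saline difference. Section 8.3 would test such a baseline difference, but section 8.4.2 gives no means of using the result.

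The stake is the width of the intervals for three secondary endpoints and, to a lesser degree, what the trial hands on to its successor. The trial exists to supply planning parameters. An unadjusted test supplies only the raw SD, whereas a full-scale trial analysed with adjustment would need the residual SD.

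**Working it through.** **The plan's own figure.** 30 + 30 = 60. No alpha, power, effect size or SD is given, so there is no power calculation to reproduce.

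**Inputs**
- N = 60, 1:1 (section 8.1), taken as the number analysable.
- p, the number of covariate terms: 1 for BMI, 2 for height and weight entered separately.
- R², the within-arm share of outcome variance that the covariates explain. The documents do not give it. Assumed range: 0 to 30%.

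**Formula.** Expected variance of the adjusted group difference, relative to the unadjusted one:

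V = (1 − R²) × (N − 3)/(N − 3 − p)

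The second factor is the cost of estimating the covariate effects. It is 57/56 = 1.018 for p = 1 and 57/55 = 1.036 for p = 2. The gain in equivalent subjects is 1/V − 1, and the interval width changes by about √V.

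| Assumed R² | V, p = 1 | Width, p = 1 | Subjects, p = 1 | V, p = 2 | Subjects, p = 2 |
|---|---|---|---|---|---|
| 0 | 1.018 | +1% | −2% | 1.036 | −4% |
| 10% | 0.916 | −4% | +9% | 0.933 | +7% |
| 20% | 0.814 | −10% | +23% | 0.829 | +21% |
| 30% | 0.713 | −16% | +40% | 0.725 | +38% |

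Example, p = 1 and R² = 20%: 0.80 × 57/56 = 0.814; 1/0.814 − 1 = 23%; √0.814 = 0.902.

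**Break-even.** V = 1 when R² = p/(N − 3): 1/57 = about 2% for one covariate and 2/57 = 3.5% for two. For four terms (for example height, weight and a three-level segment) it is 4/57 = 7%.

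**Simulation check.** Two covariates, 30 per arm, an assumed true difference of 0.5 SD, two-sided 5% level, 8,000 runs per case:

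| R² | Power, unadjusted | Power, adjusted |
|---|---|---|
| 0 | 48% | 46% |
| 10% | 47% | 50% |
| 30% | 48% | 61% |

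At R² = 30% the standard deviation of the estimate fell from 0.258 to 0.220. The squared ratio is about 0.73, in line with the formula. The 0.5 SD difference is illustrative only, because the plan has no target difference.

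**Is segment a baseline covariate?** Section 5.1.4 and the schedule list planning after randomization, both at Visit 2. Section 3.5 says the investigator learns the arm at that visit. Section 5.2.5 requires only that planning come before localization. The segment could therefore be chosen with the arm known. Height and weight do not raise this question.

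**Fewer than 60 analysable.** Section 5.2.5 says secondary outcomes need not be recorded after a dural puncture. Section 6.2 allows up to 5 such subjects before its stopping rule applies. With 55 subjects and p = 1 the cost factor is 52/51 = 1.020, so the table barely changes. Adjustment does not repair any selection caused by those missing values.

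**The case against.** The strongest reply is that nothing here is wrong. Under randomization the unadjusted tests are valid, and a chance imbalance in BMI is random error that the unadjusted interval already allows for. A reader might infer that the planned comparison is biased or invalid; the documents do not support that. The primary Fisher's exact test is untouched. All of this stands, and it makes the point one of efficiency.

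A reader might also infer that precision is certainly lost. That depends on an R² that the documents never state. The case is weakest for time to identify the space: by sections 5.2.5 and 5.2.5.1 its clock starts when the syringe is attached, after the needle has gone in at least 3 cm to pass the subcutaneous tissue. Procedure duration spans repeat punctures and may depend on operator skill, which the introduction stresses. Distance has the best anatomical argument, but the plan states no hypothesis that air or saline alters it. These limits stand. They reduce the expected benefit without removing it, since break-even is about 2% for BMI alone.

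A third inference would be that the SDs passed to the full-scale trial will be too large. That is not so in general: the raw SD is the right input if that trial is analysed without adjustment. The residual SD could also be computed later from the same data.

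Finally, a reader might treat planned segment as a ready covariate because it is recorded. The order of steps does not establish that it is fixed before the arm is known, and adjusting for a choice made with that knowledge could introduce bias.

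**Conclusion.** The point holds as a modest, low-cost improvement. Section 8.4.2 leaves unused a baseline measure that the trial already collects and that plausibly explains some of the variation, most likely in distance and less certainly in the two times. If BMI explains 10%, 20% or 30% of the variance, the gain with 60 analysable subjects is worth about 9%, 23% or 40% more subjects; with height and weight entered separately it is about 7%, 21% or 38%. If body size is unrelated to outcome, variance rises by about 2% or 4% respectively. These figures rest on assumed R² values and on a linear covariate effect. The body-size adjustment stands without segment.

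**What to change.** In section 8.4.2, before any outcome data are examined:

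1. Prespecify a linear model with arm and baseline BMI for skin-to-epidural distance, and for the logarithm of time to identify the space and of procedure duration.
2. Report the adjusted difference (distance) or ratio (times) with its 95% CI, and keep the planned unadjusted test alongside.
3. Add planned insertion segment only if it is fixed and recorded before the randomization envelope is opened. If so, define its categories in advance, since each extra term adds to the cost shown above.
4. Report both the raw within-arm SD and the residual SD, on the scale analysed, so that the full-scale trial can use the one that matches its own analysis.
5. State how many subjects contribute to each model.

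The cost is SAP wording and a few lines of code, with no new data for the BMI model. The statistical downside is the 2% rise in variance if BMI proves unrelated to outcome.

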8.5. Safety Assessment

Incidence of the adverse events will be summarized. In the case of CTCAE grade summaries, the most severe event will be presented in summary tables in the case of multiple occurrences per patient. The frequency and the percentage of each category will be presented. All safety parameters, including adverse events, adverse device effect, serious adverse event, serious adverse device effects and unanticipated adverse device effect will be listed by A and S groups. The Medical Dictionary for Regulatory Activities (MedDRA) adverse event dictionary will be used to map verbatim adverse events to preferred terms and system organ class. Fisher's exact test will be applied for comparing the incidences of adverse events between treatment groups.

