1. INTRODUCTION

Locating the epidural space is an indispensable part of obstetrical analgesia, surgical anesthesia, postoperative analgesia, and chronic pain control.

The traditional method of locating the position of the needle tip is loss of resistance technique (i.e., the

"LOR"), which is based on detecting the pressure drop occurring at the moment the needle tip reaching the epidural space. Because the pressure of the epidural space is lower than the cavities of others tissue, a free injection of air or liquid from the syringe can be induced, resulting in a sudden loss of resistance of the plunger. Thus, the anesthesiologist can detect the pressure drop by feeling the resistance of pushing the plunger of the attached syringe.

The epidural space is a very thin area near the spinal cord. The advance of needle must be stopped right after the needle tip reaches the epidural space to prevent accidental dural puncture, which may lead to cerebrospinal fluid leakage followed by intractable headache and injuries of the spinal nerves. However, the current incidence rates of accidental dural punctures are 0.19-3.6%¹.

Using the LOR hand feeling to locate epidural space relies on manual skill of the operator and the considerable experiences. Choosing air or saline for LOR technique depends on personal experiences of the operator. The variety of LOR techniques has increased the difficulty of learning².

Some objective and confirmatory devices based on LOR technique are developed, such as Episure and Epidrum, and have been discuss under clinical trial³⁻⁵. The results show a lower failure rate and a shorter time needed to identify the epidural space. However, the restriction of the media and the actuating pressure selection will deprive the anesthesiologists' habit.

The EpiFaith syringe is an improved LOR device with the ability to warn and help physicians to achieve the safe insertion is required. EpiFaith syringe provides objective, and quantitative pressure information as well as a visual signal which is triggered at the moment the needle tip enters the epidural space. Hence, the anesthesiologist can get a clear endpoint for the advancing of the needle easily. The advantages of EpiFaith syringe including that the anesthesiologist can control the epidural needle with both hands and achieve the real- time pressure detection.

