3.2. Study Population

3.2.1. Subject number

Recruitment will stop when approximately 60 subjects are included.

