3.4. Method of Assigning Subjects to Treatment Groups

Subjects will be randomized to one of the two groups (A group – EpiFaith syringe with air or S group – EpiFaith syringe with saline) at the ratio of 1:1. The randomization method will result in sealed, opaque envelopes containing the computer- generated, random assignment. Randomization will occur in blocks so that blocks of equal numbers of subjects will be used to avoid potential runs of assignments. The randomization code will be generated specifically for each center.

Screening number will be assigned once subject signed the inform consent. Only eligible subjects at Visit 2 will receive a randomization number at randomization. The subject will receive the

corresponding test devices assigned in the randomization envelope according to the randomization number. The number will be maintained by the investigator throughout the study. For any reason that a subject withdraws from the study prematurely after the randomization, his/her randomization number will not be reused. The next eligible subject will receive the lowest available randomization number.

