6.2. Data Safety Monitoring Plan

An Independent safety monitor (anesthesiologist) will call for terminating the study early if more than 5 subjects experience inadvertent dural puncture.

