7. STUDY ENDPOINTS

7.1. Primary Endpoint

• Success of epidural localization

(defined as the catheter can be inserted into epidural space successfully, no cold perception in the blocked dermatomes after the injection of anesthetic by cold sensation test, and no occurrence of inadvertent dural puncture.)

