8.4.1. Analysis of primary endpoint

The primary endpoint is the success of epidural localization. The primary analysis will be conducted by Fisher's exact test.

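### Section 8.5 gives inadvertent dural puncture a nearly uninformative air-versus-saline test and percentages by group, but no pooled rate for the syringe and no confidence interval

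*Combined protocol and SAP*

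**What the plan says.** All references are to the combined protocol and SAP.

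- **Safety analysis (8.5).** Adverse event incidence is summarised with frequencies and percentages, safety parameters are listed by air (A) and saline (S) group, and "Fisher's exact test will be applied for comparing the incidences of adverse events between treatment groups". No confidence interval and no total over both groups is mentioned.
- **Stopping rule (6.2).** An independent safety monitor "will call for terminating the study early if more than 5 subjects experience inadvertent dural puncture". No arm is named, so I read the count as pooled. No other event appears in the rule.
- **Primary endpoint (7.1).** Success requires, among other things, "no occurrence of inadvertent dural puncture". A puncture therefore counts as a failure of localization, together with catheter failure and persisting cold perception.
- **Background rate (1, Introduction).** The text gives puncture as the reason needle advance must stop promptly, and says "the current incidence rates of accidental dural punctures are 0.19-3.6" per cent.
- **Size.** Section 8.1: "A total of 60 subjects (30 subjects per group) will be required in this study", to obtain parameters for a full-scale trial. Section 3.2.1: "Recruitment will stop when approximately 60 subjects are included".
- **Safety set (8.2).** Everyone who received a study device, grouped by treatment actually received.
- **Test level.** Section 8.4.1 says "The primary analysis will be conducted by Fisher's exact test". Neither there nor elsewhere is an alpha or a sidedness given.

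**The concern.** Dural puncture is the harm this device is meant to help avoid and the only one that can stop the trial, but its planned analysis does not fit what the trial can learn about it.

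First, the contrast. Both arms use the same syringe and differ only in the medium. A comparison of A with S can inform the choice of medium. It cannot show how often puncture occurs with the syringe, and that is the figure a reader would set beside the range quoted in the Introduction.

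Second, the test. With about 30 per arm and a rare event, a Fisher p-value will almost always be non-significant, even if one medium were materially worse. Such a result is easily misread as reassurance.

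Third, the purpose. Section 8.1 presents the trial as a source of parameters for a larger one. That is an estimation aim, served by a rate with an interval rather than by a p-value.

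**Working it through.** **Inputs.** 30 per arm (8.1). Termination called for at the 6th puncture (6.2: more than 5). Background rate 0.19% to 3.6% (Introduction). Two-sided 5% is my assumption, and one-sided results are shown as the range. The planned 60 rests on a cited pilot-size recommendation, with no alpha, power or event rate, so there is no planned figure to reproduce.

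**1. Smallest p-value at 30/30.** If all k punctures fall in one arm, the one-sided Fisher p is C(30,k)/C(60,k). With equal arms the two-sided p is twice that.

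| Split | Two-sided p |
|---|---|
| 4 v 0 | 0.112 |
| 5 v 0 | 2 × 142,506 / 5,461,512 = 0.0522 |
| 6 v 0 | 2 × 593,775 / 50,063,860 = 0.0237 |

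Enumerating every split with five or fewer punctures in total, the smallest two-sided p is 0.0522. At 30/30, p<0.05 therefore needs at least six punctures, which is when 6.2 calls for termination.

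**2. How firm that limit is.**

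- One-sided at 30/30, 5 v 0 gives 0.026.
- With arms of 29 and 30 and all five events in the smaller arm, the tail is C(29,5)/C(59,5) = 118,755 / 5,006,386 = 0.0237. The mirror-image split (all five in the larger arm) has probability 0.0285, which is higher, so the two-sided test does not add it and p stays at 0.0237.
- The same pattern gives 0.0217 at 29/31 and 0.0240 at 30/31.

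None of these triggers 6.2.

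**3. Power of the two-sided Fisher test**, summed over both binomial distributions.

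| True rates | Power, 30/30 | Power, 29/30 (higher rate in the arm of 29) |
|---|---|---|
| 3.6% v 7.2% | 0.7% | 2.0% |
| 3.6% v 10.8% | 3.8% | 8.0% |
| 3.6% v 15% | 13% | 21% |

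**4. Events to expect.** 60 × 0.0019 = 0.11 and 60 × 0.036 = 2.16 punctures. At 3.6%, the chance of six or more in 60 is 2.1%.

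**5. What an interval would show** (Clopper-Pearson 95%). For zero events the upper limit is 1 − 0.025^(1/n).

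| Punctures | Rate | 95% interval |
|---|---|---|
| 0/30 | 0% | 0 to 11.6% |
| 0/60 | 0% | 0 to 6.0% |
| 2/60 | 3.3% | 0.4 to 11.5% |
| 5/60 | 8.3% | 2.8 to 18.4% |

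With no events, pooling roughly halves the upper limit. Even then 3.6% lies inside the interval.

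**The case against.** The strongest reply is that this is a pilot. Low power for a rare harm is normal at this size, air versus saline is the randomised contrast, and a between-arm test accompanied by descriptive incidence matches the design. That stands: the test is not wrong, only weak for this event.

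Three stronger readings are tempting, and the documents support none of them.

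- *The test can never be significant before the stopping rule fires.* This needs exactly 30/30 and a two-sided 5% test. Alpha and sidedness are unstated, recruitment is to about 60, the block size is not given and the safety set is as treated. A one-subject imbalance is enough to bring 5 v 0 to p=0.024. Five or six punctures all in one arm is also a remote outcome at the quoted background rates.
- *The puncture rate is never estimated.* Section 8.5 plans frequencies and percentages, so crude per-group rates will appear if punctures are recorded as adverse events, and a reader could add the two counts. What is absent is a named line, a pooled figure and an interval.
- *The sponsor plans to claim equal safety.* No section says so. The misreading is a risk, not a stated intention.

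It is also fair to say that the benchmark is imperfect. The reference cited for it concerns obstetric practice, whereas this trial enrols surgical patients. That argues for caution in any comparison with 0.19% to 3.6%, but not against giving an interval.

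**Conclusion.** The concern holds in a limited form. For inadvertent dural puncture, the planned Fisher comparison carries almost no information: power is 0.7% for a doubling from 3.6% and 13% for 3.6% v 15%, at 30/30 and an assumed two-sided 5%. Under the same conditions, significance lies just beyond the number of punctures that 6.2 tolerates (0.052 at five, 0.024 at six). That coincidence depends on exactly equal arms and should be described as a near-limit. A p-value that moves from 0.052 to 0.024 with the loss of one subject from one arm is itself a poor basis for a safety statement.

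The gap that depends on no assumption about alpha is that the plan has no pooled device-level puncture rate and no interval, pooled or per arm. Closing it is an inexpensive improvement in reporting. It does not invalidate the design or the primary analysis.

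**What to change.** In 8.5:

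1. Report inadvertent dural puncture as its own line, for both arms pooled and for each arm, with exact (Clopper-Pearson) 95% intervals. Use the safety set already defined in 8.2; no new denominator is needed, and 7.2 need not gain an endpoint.
2. For this event, replace the Fisher p-value with the A-minus-S difference in rates and a 95% interval, by a method named in advance that copes with zero counts (Newcombe's, for example).
3. Add a sentence that a non-significant adverse event comparison will not be presented as evidence of equal safety.

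The cost is some SAP wording and one extra table, with no new data or subjects. The price in interpretation is a more modest conclusion, because the best possible result, 0/60, still leaves an upper limit of 6.0%.
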